Is WALANT Applicable in Distal Radius Fracture Osteosynthesis?

Study Protocol and Statistical Analysis Plan

October 2020

NCT (still not available)

ABSTRACT

Title → Is WALANT Applicable in Distal Radius Fracture Osteosynthesis?

Aims → To evaluate is Wide Awake Local Anaesthesia No Tourniquet (WALANT) is applicable to distal radius fracture (DRF) osteosynthesis and possible benefits of not using the ischemia cuff in distal radius osteosynthesis, by using the WALANT anaesthetic technique and compare it with patients who have undergone the current anaesthesia method (locoregional anaesthesia with or without sedation)

Material and methods → Randomized controlled study comparing patients operated on for distal radius fracture with osteosynthesis during a year (December 2020 to December 2021). The randomization will be done by 10 block in order to ensure similar numbers of patients in both groups of intervention. In the group A patients will be operated on with local anaesthesia (lidocaïne + adrenaline + bicarbonate) with or without sedation without the use of ischemia, while in group B patients will be given anaesthesia by proximal locoregional blockade with or without sedation and ischemia cuff. Immediate short-term results will be compared between both groups. Primary outcomes will be preoperative and postoperative pain, pre and postoperative swelling, and patient and surgeon satisfaction.

Results →

Conclusion →

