2.2. SECONDARY OUTCOMES

1. Evolution of the surgical wound (active bleeding and dressing condition at 24 hours and 10-15 days after surgery)
2. Postoperative mobility
 - a. Thumb mobility and opposition (Kapandji scale)
 - b. Finger mobility (capability of the patient to arrive at proximal and distal palm crease)
 - c. Wrist mobility (flexion, extension, pronation, supination, ulnar deviation, radial deviation)
3. Surgeon's technical difficulty.
 - a. Scale 1-5 (1 easy- 5 difficult)
 - b. Intraoperative stress /yes/no) and reason
4. Insufficient anaesthesia
 - a. Need of change to General Anaesthesia
 - b. Need of adding more anaesthesia
 - i. Type of anaesthesia used (sedation, local anaesthesia reinforcement, etc.)

- ii. Reason for change
- 5. Postoperative complications (total number and description)

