3.3. VARIABLES

Independent variables:

These variables will be collected during the surgery and in the subsequent from patient anamnesis, clinic history and filling the Collection Data Guide Form:

- Age (years)
- Sex (male / female)
- Dominant hand (left / right / both)
- Injured hand (left / right / two)
- Fracture classification according to American Orthopaedic (AO) (16), (17)
- Number of days from injury to surgery (days)
- Preoperative pain (VAS scale (18))
- Preoperative swelling injured hand and healthy hand. The perimeter of the wrist will be measured at the height of the proximal palmar fold in cm.

Dependent variables:

These variables are the ones we want to study and will be collected during the surgery and afterwards from patient anamnesis, clinic history and filling the Collection Data Guide Form:

- Duration of admission (hours).
- Duration of surgery (minutes).
- Duration of ischemia in group B (minutes).

- Preoperative and postoperative pain (VAS scale): Pain at baseline, 24 hours post-intervention, at the visit of the first treatment 10-15 days post-intervention and pain 1 month after the intervention.
- Intraoperative pain (VAS scale): Assessable only if it has not required sedation.
- Time (minutes) of anaesthesia administration
- Time (minutes) from the end of administration to the beginning of IQ
- Need for anaesthetic reinforcement:
 - Sedations (yes/no) and reason
 - In the case of WALANT: Taking into account the reference technique used (10), if any extra doses are needed and location within the wrist
- Postoperative analgesia during admission and discharge (drugs used, dose and frequency of use)
- Postoperative swelling injured hand and healthy hand (cm).
- Stained dressing and the presence of active bleeding due to the wound within 24 hours and during the first outpatient clinic 10 or 15 days after surgery.
- Patient satisfaction during the first outpatient clinic 10 or 15 days after surgery. → Assess satisfaction (1-5) / Would you repeat the anaesthesia type? / Would you recommend the technique?
- Description of the complications of anaesthesia.
- Description of postoperative complications.
- Mobility 24 hours post-intervention, first aid and one month later. (The mobility of the fingers, intrinsic and extrinsic muscles, Kapandji exercises 1-10 and wrist mobility will be assessed by measuring flexion-extension and prone-supination with a goniometer).
- Surgeon's experience

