 - a. Technical difficulty due to lack of visualization in the surgical field (Scale 1-5. 1 no difficulties, 5 very difficult))
 - b. Added stress to the surgery (yes/no) and reason.

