3.4. DATA COLLECTION AND INSTRUMENTS

A sample of patients with a distal radius fracture operated in our Hospital will be obtained. Those who meet the inclusion criteria will be asked to participate and will be told what the study is about. Those who accept must sign the specific informed consent of this study.

Prior to surgery, an external observer will collect the personal data of the patients, assign them a code (P1, P2, P3...) and perform the anamnesis following the Data Collection Guide Form

Patients' recruitment will be done during a year, from December 2020 to December 2021. They will be separated into two groups. The external observer will do this process with 10-block randomization using Study Randomizer (2017), a web based randomization service (19)

The first (Group A) in which WALANT technique will be performed and the second (Group B) in which locoregional anaesthesia (either axillary or supraclavicular block) with axillary ischemia will be applied. Because it is considered a long-term intervention, all patients will be offered the option of sedation or not, and this variable may change depending on the criteria of anaesthesia or the patient himself in order to facilitate their well-being. All patients participating in the study will receive the same antibiotic prophylaxis following our protocol (Cefazolin 1g iv in <80Kg or 2g 80-160Kg and in patients with normal renal function, to pass in 5 minutes. In those with FG The dose should be adjusted, and a second dose of 2g iv should be given if the surgery lasts 3 hours or more. In patients with penicillin allergy, Teicoplanin 600mg iv will be administered in 10 minutes, without repeating the dose. in no case) (20)

Group A (WALANT Anaesthesia +/- sedation + NO ischemia)

In WALANT technique, the doses are followed according to Lalonde's (21). 1% lidocaine with 1: 100,000 adrenaline is generally used to counteract the acidic pH of lidocaine, which is buffered with 8.4% (1M) sodium bicarbonate in a 10: 1 ratio to decrease pain during administration. If more volume is required, Lidocaine is diluted to 0.5% so as not to exceed the maximum toxic dose of 7mg / kg with a maximum total dose of 500mg (50ml of 1% Lidocaine or 10cc of 5% Lidocaine) (22)

In this case, the preparation will be made by the nurse with 100cc of SF, from which 15cc will be extracted and 10cc of 5% Lidocaine + 1cc Adrenaline + 4cc of 1M Bicarbonate will be added.

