Anaesthesia will be administered in the operating room, monitoring the patient's HR, BP, and SatO2. It will take 20-30 minutes before starting the surgery, as the peak of vasoconstrictor action of the adrenaline is reached after this time.

The technique according to Ahmad (10) is to infiltrate 40ml of local anaesthetic preparation, distributing 10ml to the subcutaneous tissue along the approach, from proximal to distal. Subsequently, 30ml is administered in deeper planes divided into

3 points, from proximal to distal, distributed in 4ml around the flying periosteum, 2ml radially and 4ml in the dorsal periosteum, through a lateral entrance, introducing the 'needle from the radial side avoiding puncturing through the radial artery. An additional 10ml will be added for the intra-articular region, using conventional 3-4 and 6R arthroscopy radiocarpal approaches. In some cases it may be increased if the surgeon considers that it requires more volume, as long as we do not exceed the toxic doses (23).

In patients with a history of cardiac pathology, it is possible to assess the possible dissolution of adrenaline at 1: 400000, this group will include those patients with ischemic heart disease and / or severe hypertension (irregular hypertension with the use of 3 different antihypertensive drugs).

Group B (Locoregional anaesthesia proximal block +/- sedation + ischemia)

The anaesthesiologist in charge of the operating room will perform the locoregional block. The same ischemia sleeve (size, brand, manufacturer and country of origin) will be used on all patients and the same ischemia pressure (250mmHg) will be applied.

In all of them, intraoperative monitoring will be performed, which will be the same in both groups, the FC, FR, TA, ECG, SatO2 and duration of the intervention must be recorded.

The surgical procedure will be the same for all patients. If the surgeon considers it necessary, arthroscopic assistance will be used with conventional dorsal radiocarpal portals (2-4R and 6R). Surgeons from the surgeons of our Upper Extremity Unit will perform all operations.

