3.6 STATISTICAL PLAN

Quantitative values will be described as mean and standard deviation in case of normal distribution, or with median and interquartile range otherwise. Qualitative variables will be described with absolute and relative frequencies. The Student's t test for normal quantitative variables and the non-parametric Mann-Whitney U test will be used to compare the two experimental groups. Pearson's chi-square test for expected frequencies above 5 and Fisher's exact test would be used to compare the distribution of qualitative variables between groups. Statistical program R [ref] will be used, applying a statistical significance level of 5%.

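### Several surgeons operate and apparently score difficulty themselves, but surgeon identity is not a listed variable, is not fixed before allocation and is not used in the analysis

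*Combined protocol and SAP*

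**What the plan says.** **Who operates.** Section 3.4: "Surgeons from the surgeons of our Upper Extremity Unit will perform all operations". The number of surgeons, their experience and the way cases are shared out are not given.

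**What they rate.** Section 2.2 lists "Surgeon's technical difficulty" as a secondary outcome, scored 1-5, together with a yes/no stress item. In section 3.3 both items sit under the heading "Surgeon's experience", and the scale is defined as "Technical difficulty due to lack of visualization in the surgical field (Scale 1-5. 1 no difficulties, 5 very difficult". No independent rater is named. The abstract goes further and puts the surgeon's view among the primary outcomes: "Primary outcomes will be preoperative and postoperative pain, pre and postoperative swelling, and patient and surgeon satisfaction". Section 2.1 does not.

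**What is recorded.** Section 3.3 lists no surgeon identity, seniority or case volume. The heading just quoted covers only the two ratings.

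**Allocation.** Section 3.4: "The external observer will do this process with 10-block randomization using Study Randomizer (2017), a web based randomization service (19"). No stratification factor is named, and nothing says when the surgeon is chosen relative to allocation.

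**Analysis.** Section 3.6 uses Student's t test "for normal quantitative variables and the non-parametric Mann-Whitney U test will be used to compare the two experimental groups", with Pearson's chi-square or Fisher's exact test for qualitative variables. There is no surgeon term or stratum.

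**Limitations.** The limitations section accepts that block doses vary with the anaesthesiologist on duty and that the sample may be small. It does not mention variation between surgeons.

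**The concern.** On a subjective five-point scale, each operating surgeon is a different rater, and that rater cannot be blinded to whether a tourniquet is in use. Randomising patients balances patient characteristics. It balances surgeons only if the surgeon is fixed before the arm is known, or is chosen without regard to it.

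The hypothesis in the introduction includes the claim that WALANT does not make the procedure technically harder for the surgeon. If group A cases tended to go to surgeons who are comfortable with WALANT, or who simply score low, the arms could look alike, or WALANT easier, for that reason alone. The comparator is described as current practice, so unequal familiarity with WALANT is plausible. Surgery duration also depends on who operates. Pain, swelling and patient satisfaction are much less exposed.

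**Working it through.** The plan gives no sample size, SD or effect size, so there is no figure of its own to reproduce. Everything numerical below is an illustration on stated assumptions.

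**Assumptions.** Four surgeons; between-surgeon SD 0.6 points; within-surgeon SD 0.9 points; 30 patients per arm; no true difference between arms; two-sided 5% test. Steering means that the two lower-scoring surgeons do a share q of group A and 1 − q of group B.

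**Step 1: bias under steering.**
- Bias = (expected gap between the upper and lower surgeon pairs) × (difference between arms in the lower pair's share).
- With four surgeons and SD 0.6, the expected gap is about 0.80 points.
- q = 0.65: 0.80 × (0.65 − 0.35) = 0.80 × 0.30 = 0.24 points.
- q = 0.75: 0.80 × (0.75 − 0.25) = 0.80 × 0.50 = 0.40 points.

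**Step 2: false-positive rate (simulation, 4,000 trials per row).**

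| Steering | Bias, A − B | Pooled test | Surgeon as a factor |
|---|---|---|---|
| 65/35 | −0.24 | 14.9% | 5.2% |
| 75/25 | −0.40 | 32.5% | 4.4% |

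An independent repeat with 5,000 trials gave 15.2% and 32.3% pooled, against 4.9% and 5.6% adjusted. Rounding the scores to whole points from 1 to 5 gave 14.7% and 31.0% pooled.

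**Step 3: no steering.** The pooled test keeps its level. In a separate simulation with two surgeon groups whose means differ by g = 0.5 or 1.0 within-surgeon SD, and 20, 30 or 50 patients per arm, the rate was 4.8% to 5.1%. What is lost is precision. In the four-surgeon setting the SD of the arm difference was 0.271 pooled and 0.242 adjusted, so the variance ratio is 0.242² / 0.271² = 0.0586 / 0.0734 = 0.80. The repeat gave 0.76.

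**Step 4: sensitivity.** In the two-group simulation, let d be the difference between arms in one group's share of cases. The bias is g × d.
- 30 per arm, d = 0.4: bias 0.2 SD with 11.7% false positives (g = 0.5), or 0.4 SD with 28.6% (g = 1.0).
- All cells with d from 0.2 to 0.6: from 6.1% (20 per arm, g = 0.5, d = 0.2) to 78.8% (50 per arm, g = 1.0, d = 0.6).

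**Step 5: chance imbalance.** If one surgeon group does half the cases and choice is independent of arm, the arms differ by 20 percentage points or more in that group's share in about 27%, 15% and 6% of trials with 20, 30 and 50 patients per arm. The 5% level already allows for this on average, but in a given trial one would want to see it.

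**The case against.** The strongest reply is that several surgeons in one unit do not confound a randomised trial. Bias needs surgeon choice to depend on the arm, and the documents give no sign that it does. That stands: without steering the pooled test is valid, and the 15% and 33% figures belong to an unfavourable case in which steering lines up with scoring tendency. Steering unrelated to scoring would have no systematic direction, and steering by seniority or complexity could work against WALANT.

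Four stronger readings are tempting, and the documents do not support them:
- A reader might infer that the arms are confounded. The text shows only that confounding is not prevented.
- A reader might suppose that surgeons see the allocated arm on a theatre list and pick cases. No such list is mentioned. The external observer acts before surgery, and the surgeon may already be fixed by then.
- A reader might conclude that an imbalance could never be detected or corrected. The data collection form is not among the documents and may hold a surgeon field, and clinical records may identify the operator. The supportable statement is that surgeon identity is not a listed variable.
- A reader might extend the point to anaesthetic reinforcement in general. Section 3.4 leaves sedation to the anaesthesia team or the patient, and the anaesthesiologist performs the group B block. Only extra WALANT volume is said to be the surgeon's decision.

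It is also fair that section 2.2 places difficulty and stress among the secondary outcomes, and that self-rating, though the natural reading, is not stated outright. These points limit the reach of the concern. They do not remove the gap in recording, allocation and analysis.

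**Conclusion.** The point holds as a gap in safeguards, not as a demonstrated bias. It bears mainly on difficulty, stress and surgery duration. How large the effect could be depends on the number of surgeons, how differently they score and how far surgeon choice follows the arm, none of which the documents give. It ranges from no effect on the error rate without steering to a bias of about 0.24 to 0.40 points under the four-surgeon assumptions. The case for acting does not need steering to occur: a within-surgeon comparison is more precise by about 20% in variance under the same assumptions, and it protects the claim of no added difficulty if steering or a chance imbalance does arise. It is a worthwhile, inexpensive improvement, held with medium confidence.

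**What to change.** 1. In section 3.4, require the operating surgeon to be named before the randomiser is opened, and any later swap to be noted.
2. In section 3.3 and on the data form, add a surgeon code, and state that the operating surgeon gives the difficulty and stress ratings. A running count of each surgeon's WALANT cases is optional.
3. In section 3.6, add a surgeon-by-arm table and within-surgeon comparisons: a van Elteren test for difficulty, a Cochran-Mantel-Haenszel test for stress, and surgeon as a factor for surgery duration. Report the pooled tests alongside.

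This needs no extra patients or staff, and no stratification of the randomisation by surgeon, which may be impractical in a small trial. The cost is a little more recording and analysis. Some degrees of freedom are lost: with four surgeons and 60 patients, residual degrees of freedom fall from 60 − 2 = 58 to 60 − 5 = 55. The loss is greater if many surgeons do few cases each.

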3.5 LIMITATIONS OF THE STUDY

- The sample size (N) may be small.
- VAS scale is a subjective measure and therefore makes it difficult to compare different patients. However, to date, there are no objective pain assessment scales that meet this purpose.

- The doses of anaesthesia used in the proximal block will not be the same in all patients and depend on the anaestheologist in charge of the operating room in that moment.

- Heterogeneity of fractures may vary the results of the study, as more complex fractures can cause more pain.

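### The plan names fracture complexity as a driver of pain and collects AO class, but compares the primary pain outcome only with unadjusted tests; a prespecified adjusted model would recover some precision at almost no cost

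*Combined protocol and SAP*

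**What the plan says.** Section 3.5 (Limitations of the study) states: "Heterogeneity of fractures may vary the results of the study, as more complex fractures can cause more pain". The same list concedes that the number of patients may turn out small. Pain is the first primary outcome in section 2.1, defined as the change from the preoperative score at 24 hours, 10–15 days and 1 month.

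Section 3.3 lists among the independent variables "Fracture classification according to American Orthopaedic (AO) (16), (17"), next to preoperative pain and swelling.

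On allocation, section 3.4 says: "The external observer will do this process with 10-block randomization using Study Randomizer (2017"). The abstract gives the purpose: "The randomization will be done by 10 block in order to ensure similar numbers of patients in both groups of intervention". No stratification factor is named in either place.

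On analysis, section 3.6 says: "The Student's t test for normal quantitative variables and the non-parametric Mann-Whitney U test will be used to compare the two experimental groups". For categorical variables: "Pearson's chi-square test for expected frequencies above 5 and Fisher's exact test would be used to compare the distribution of qualitative variables between groups". It contains no regression model, ANCOVA, stratified test or analysis by AO class.

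Section 3.2 excludes open fractures, polytrauma and associated fractures needing further fixation, but does not restrict AO class.

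**The concern.** The plan identifies a prognostic factor for its first primary outcome, records it, and then uses it neither at allocation nor in the analysis. Blocking balances the number of patients per arm, not their fracture type. The chi-square or Fisher test could show that AO class is unevenly distributed, but cannot correct the pain comparison for it.

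Two things are at stake. First, in the one trial that will be run, complex fractures may fall more often in one arm and move the estimated pain difference for reasons unrelated to the anaesthetic. Second, variation in pain due to fracture type stays in the error term, although the data to remove it are already collected. Adjusting only after an imbalance has been seen would be open to challenge as data-driven, so the model needs to be written down beforehand.

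**Working it through.** The documents give no sample size, power, effect size or standard deviation, so there is no stated figure to reproduce. The inputs below are assumptions, shown over a range: equal arms of n = N/2; share of complex fractures p = 0.3 or 0.5; difference in outcome between complex and simple fractures D = 0.25, 0.5 or 1.0 within-class SD; treatment effect 0.5 SD; two-sided 5% level (section 3.6 gives 5% but not the sidedness).

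**1. Chance of an imbalance of at least 20 percentage points.** The complex fractures per arm are taken as two independent binomial counts (n, p). The SD of the difference in shares is √(2p(1−p)/n); for n=30 and p=0.5 it is √(0.5/30) = 0.129. Exact binomial results:

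| N | p = 0.3 | p = 0.5 |
|---|---|---|
| 40 | 22.6% | 26.8% |
| 60 | 12.0% | 15.5% |
| 100 | 3.8% | 5.7% |
| 200 | 0.3% | 0.6% |

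**2. What such an imbalance does to the estimate.** Shift = imbalance × D. At exactly 20 points this is 0.20 × 0.5 = 0.10 SD, or 0.20 × 1.0 = 0.20 SD. With p=0.5 the total SD is √(1 + 0.25D²), that is 1.031 for D=0.5 and 1.118 for D=1.0. The standard error of the arm difference is total SD × √(2/n).

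| N | Shift / SE, D=0.5 | Shift / SE, D=1.0 |
|---|---|---|
| 40 | 0.10/0.326 = 0.31 | 0.20/0.354 = 0.57 |
| 60 | 0.10/0.266 = 0.38 | 0.20/0.289 = 0.69 |
| 100 | 0.10/0.206 = 0.49 | 0.20/0.224 = 0.89 |

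The shift stays below one standard error throughout.

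**3. Validity of the planned test.** In simulation with no treatment effect (p=0.5, 40,000 trials per setting), the t test's overall type I error was 4.9–5.1% for N = 40, 60 and 100. Among only those trials with an imbalance of at least 20 points, it was 6.3% (D=0.5) to 11.2% (D=1.0) at N=60, and 7.9% to 16.6% at N=100. At N=100 such trials are rare (step 1).

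**4. Gain from adjustment.** The variance explained by class is R² = p(1−p)D² / (1 + p(1−p)D²). This gives 1.3–1.5% for D=0.25, 5.0–5.9% for D=0.5 and 17.4–20.0% for D=1.0. Residual SD becomes √(1−R²).

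| | Power, N=60 | Power, N=100 |
|---|---|---|
| Unadjusted | 49.1% | 70.5% |
| D=0.25 | 49.6–49.7% | 71.1–71.2% |
| D=0.5 | 51.1–51.4% | 72.7–73.1% |
| D=1.0 | 56.8–58.1% | 78.5–79.8% |

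The sample-size equivalent is 1/(1−R²): 1/0.95 = 1.05 and 1/0.80 = 1.25, so about 5–25% more patients for R² of 5–20%. For 80% power at 0.5 SD, n per arm falls from 63 to 60 (63 × 0.95 = 59.9) or to 51 (63 × 0.80 = 50.4). These figures ignore the small cost of estimating extra coefficients, so at D=0.25 there is effectively no gain.

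**The case against.** The strongest reply is that nothing is broken. Unstratified blocks with unadjusted tests are a valid, conventional design, and chance imbalance is part of the sampling error that the t test already allows for. Step 3 of the working confirms this. A reader might infer that the pain comparison is biased or the test invalid; the documents do not support that, because allocation is randomised.

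Four further objections stand in part.

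- **Change scores.** The primary pain outcome is a change from the preoperative value. Any part of the complexity effect that is stable over time cancels, and section 3.5 speaks of more pain, not of a different change in pain. An effect on postoperative pain beyond baseline would remain.
- **Overlap with baseline.** Complexity that already raises preoperative pain is partly captured by preoperative VAS. The 5–25% therefore cannot be counted in full on top of baseline adjustment.
- **Restricted heterogeneity.** The exclusions in section 3.2 remove some complex injuries, and the 30–50% share has no source in the documents. A small trial is something the plan says may happen, not a stated fact.
- **Classification.** One of the plan's own references on AO class has a title saying that these fractures are hard to classify. Misclassification would shrink the gain, and whether a two-level grouping reduces it cannot be shown from the documents.

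What these objections do not answer is that the plan names this factor itself and already collects it.

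**Conclusion.** The point holds as a modest, inexpensive improvement, not as a threat to validity. The plan gives up some precision and leaves its primary pain estimate open to chance imbalance in AO class. How much depends on the sample size, the share of complex fractures and the strength of their effect, none of which is stated. A 20-point imbalance is fairly likely at N=40, uncommon at N=100 and negligible at N=200. Even when it occurs, the shift is less than one standard error in the cases computed. The gain from adjusting runs from almost nothing, if class has a weak effect, to the equivalent of about 25% more patients if it explains 20% of the variance.

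Three stronger readings are not supported:

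- **Swelling.** A reader might extend the plan's statement to swelling, but section 3.5 links complexity to pain only. The extension is plausible inference.
- **Stratification as a necessity.** It is a trade-off: two strata with blocks of 10 in a possibly small trial would leave incomplete blocks, and AO type would have to be read reliably before allocation.
- **Days from injury to surgery.** Section 3.3 collects this, but the plan nowhere calls it prognostic, so its absence from the analysis is not an inconsistency.

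**What to change.** In section 3.6, prespecify for the primary pain comparison at each time point a linear model (ANCOVA) with postoperative VAS as response, and treatment group, preoperative VAS and AO type grouped as A/B versus C as terms. Report the treatment difference with its 95% confidence interval, and the planned unadjusted test alongside it. With preoperative VAS in the model, the treatment coefficient is the same whether the response is the postoperative score or the change, so the outcome in section 2.1 need not be redefined.

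The same model may be used for swelling, with the preoperative measurement as covariate, provided the text says that the link with complexity is assumed there.

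State also that AO group is assigned from preoperative imaging. Section 3.3 says the independent variables are gathered during surgery and afterwards, and a covariate should not be open to influence from the allocated arm.

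The cost is two or three sentences and no new data. The model uses two degrees of freedom beyond the group comparison. Stratified allocation by the two AO groups is optional. If chosen, it needs blocks shorter than 10 and AO type read before allocation; the analysis change stands without it.
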